10.4. Procedures for recording and reporting adverse events

Adverse events greater than or equal to CTCAE Grade 3 will be recorded as the study team becomes aware of them. Adverse events will be reported per IRB guidelines.

11. Trial safety monitoring

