AIM 2: Determine the social, emotional, and functional burden of synkinesis, not captured in current patient-reported outcome measures as well as effect of treatment. We will analyze qualitative interviews with individual patients collected before treatment, after four of treatment, and after eight months of treatment to study the burden of disease, experience with treatment, and potential differences in both treatments. Our primary outcome is to identify the domains that may be missing from existing patient-reported measures collected in AIM 1. To do this, we will compare findings to assessment domains (i.e. decreased engagement, negative mood, etc.) in the FaCE, SAQ, and the two disease non-specific instruments, HADS and BIPQ. We will then evaluate our findings based on domains in PROMIS measures, an NIH-supported collection of validated and standardized scales.

AIM 3: Quantify the disruption in social functioning caused by synkinesis using innovative social-perceptual outcomes and emotion recognition tasks. Prior to treatment, participants will enroll in IRB Protocol 2015-0366 and complete a series of social functioning and mental health instruments and emotion expression recognition tasks. Results will be compared to control subjects without facial disability to reveal the social-perceptual impairment attributable to synkinesis. Repetition of these tasks after four months of either treatment may show improvement in recognition and emotional information interpretation when compared to initial measurements.

Figure 1: Trial overview diagram

[figure not shown]

Table 1. Schedule of activities

	Pre-treatment	Phase I	Study midpoint	Phase II	Study concludes
	Screening	Therapy or chemodenervation per standard protocol	4-month evaluation	Pragmatic trial with dual therapies	8-month evaluation
Window	>6 weeks after onset of paralysis-24 hours before treatment	Routine visits over four months	After four months	Routine visits over next four months	After four months of dual therapy
Informed Consent Obtained	X				
Randomization	X				
Enrolled	X				
Clinical Evaluation	SOC	SOC	SOC	SOC	SOC
Interviews (Audio Recorded)	X		X		X
Adverse Events Monitoring	X		X		X
Assessment of Facial Movement, Paralysis & Well-Being					
Facial Clinimetric Evaluation (FaCE) Scale (10 min)	SOC	SOC	SOC	SOC	SOC
Sunnybrook Facial Grading System (SFGS) [Video]	SOC	SOC	SOC	SOC	SOC
Synkinesis Assessment Questionnaire (SAQ) (10 min)	SOC	SOC	SOC	SOC	SOC

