Treatment and follow-up: Treatment will be performed using standard techniques in all patients. All patients will be followed by providers approximately once per month for either neuromuscular retraining therapy or botulinum toxin injection/injection evaluation over the phone, per routine clinical care. Follow-ups will provide preliminary data on treatment outcomes. Patients will also complete the SAQ and FaCE at each visit, and one month after chemodenervation as per routine protocol. Patients will undergo interviews (and tasks entailed in IRB Protocol 2015-0366) after 4 months of treatment, to determine the effects (if any) of treatment on physical, social, and emotional burden.

Patients will undergo dual therapy for four months after the initial four months. They will continue to complete the SAQ and FaCE at each care visit and will be asked to complete a qualitative interview and BIPQ and HADS instruments after 8 months of treatment.

It can be difficult to coordinate interviews with regularly scheduled patient visits. If the study team is unable to schedule these procedures on the same day, the subject will be given the option of returning on a different day of their choosing. If there are extenuating circumstances, the subject may complete the interview over the phone or via video conferencing software called WebEx. The research-only evaluations do not affect clinical care for patients.

At each time point (pre-treatment, after 4 months of treatment, and after 8 months of treatment), a trained interviewer who is not a member of the clinical staff will conduct a semi-structured qualitative interview. We will invite everyone to interview, with the goal of at least 24 patients completing interviews before treatment and after 4 months of treatment. The interview at 8 months will be optional. Interview guides were developed in consultation with clinical staff and piloted prior to use; guides include both prompted and unprompted open-ended questions aimed at understanding patient experience with various aspects of synkinesis and treatment. All interviews will be transcribed verbatim and any identifiers will be removed from transcripts prior to coding. Data will be coded using a catalogue of codes developed through analysis of emergent themes in a subset of interview transcripts. The Qualitative Core in the Wisconsin Surgical Outcomes Research Program will assist with data collection and analysis associated with qualitative aims.

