9.1. Potential risks

Risks associated with treatment

The two approaches to be compared are both widely adopted as standard of care for the treatment of synkinesis. Botulinum toxin shots have risks. These risks include, but are not limited to, infection, bleeding, bruising, weakness, pain where the shot was given, eyelid drooping, headache, nausea, flu like symptoms, dry eyes, skin rash/itching, and the chance the shot may not fully help. The FDA has issued a black box warning for the potential spread of the botulinum toxin from the site the shot was given. Very rare, serious side effects include allergic reactions, body weakness, double vision, speech issues, trouble breathing, abnormal heart rhythm, or a heart attack. While these risks are small, they can happen each time a shot is given.

Neuromuscular retraining therapy: patients may experience common side effects such as increased muscle/joint soreness or pain. There is a risk that their condition will not improve or possibly worsen. There is a risk of other problems, despite all safety measures taken. Certain underlying conditions may increase the risk and severity of problems.

Risks associated with psychological stress

Participants will be discussing their experiences and any adverse outcomes they have experienced. This may cause changes in thought processes and emotion. These changes will mostly be transitory; however they may be recurrent, or even permanent.

Risks associated with loss of confidentiality

There is a risk that information recorded about participants will be shared with people who would not normally have access to this information.

Unknown risks

This study may involve risks to the participant which are currently unforeseeable. We will inform participants as soon as possible if we discover any information that may affect the participant's health, welfare, or decision to be in this study.

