9.2. Mitigation of potential risks

Mitigation of risks associated with treatment

Subjects who would have opted to solely undergo neuromuscular retraining therapy may be exposed to risks of chemodenervation if they are randomly assigned to that procedure. These risks are described in detail to the patient as part of the informed consent process for treatment. Botox injections will be conducted according to standard clinical procedures. Subjects are not seen between Botox treatments, but they are instructed to call with any concerns, questions, or adverse reactions. Patients who are capable of carrying a fetus will be asked before each injection if they are pregnant.

Mitigation of risks associated with psychological stress

The participant showing signs of psychological stress will be reminded of the voluntary nature of the clinical trial they are participating in, and that they can stop at any time without punishment or loss of care. The Primary Investigator will be made aware of any participants displaying these signs by the research staff, and will refer them to appropriate resources as needed.

We are using the HADS and BIPQ questionnaires only for research, not to diagnose mental health issues. We will not tell patients the results. We will advise patients to contact their physician or other health care provider, such as a mental health professional, if they are experiencing emotional distress.

If imminent harm to self or others is identified from participation in the study, patients' responses and health information may be shared with others (e.g., mandatory reporting to authorities or physicians).

Mitigation of risks associated with loss of confidentiality

All information obtained and associated data files will be confidential and will be kept in a locked file or password protected computer. The risk of breach of confidentiality regarding participation in the study outside of the scope of the research will be handled by carefully controlling access to study data only to personnel on the research team.

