10.1. Adverse event definitions

Adverse event (AE)

An adverse event is defined as any untoward or unfavorable medical occurrence in a human participant including any abnormal sign, symptom, or disease temporally associated with the participant's participation in the research, whether or not considered related to the participant's participation in the research. Adverse event collection will begin at Day of Treatment Onset and continue through the last assessments. Untoward medical occurrences or acute conditions that occur between screening and surgery will be recorded as medical history.

Serious adverse event (SAE)

A serious adverse event is defined as any adverse event that meets one of the following criteria:

- Results in death; OR
- Is life-threatening; OR
- Requires hospitalization or prolongs existing hospitalization; OR
- Results in significant or persistent disability or incapacity; OR
- Results in a congenital anomaly/birth defect; OR

Unanticipated problem (UP)

An unanticipated problem is defined as an event that meets all of the following criteria:

- (1) unexpected in severity, nature, or frequency given the research procedures and the characteristics of the participant population (i.e., problems that are not described in this protocol or other study documents); AND
- (2) related or possibly related to participation in the research; AND
- (3) suggests that research places participants or others at a greater risk of harm related to the research than was previously known or recognized.

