10.2. Severity assessment and Grade

The severity of all adverse events will be assessed according to the following scale:

- Mild = does not interfere with the participant's usual function
- Moderate = interferes to some extent with the participant's usual function
- Severe = interferes significantly with the participant's usual function

The grade is assessed according to the Common Terminology Criteria for Adverse Events (CTCAE), Version 5.0.

- Grade 1: Mild; asymptomatic or mild symptoms; clinical or diagnostic observations only; or intervention not indicated.
- Grade 2: Moderate; minimal, local or noninvasive intervention indicated; or limiting age-appropriate instrumental activities of daily living (e.g. preparing meals, shopping for groceries or clothes, using the telephone, managing money, etc.)
- Grade 3: Severe or medically significant but not immediately life-threatening; or hospitalization or prolongation of hospitalization indicated; or disabling; or limiting self-care activities of daily living (e.g. bathing, dressing and undressing, feeding self, using the toilet, taking medications, not bedridden, etc.)
- Grade 4: Life-threatening consequences; or urgent intervention indicated.

- Grade 5: Death related to AE.

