11.1. Data Safety Monitoring Plan

The type of data or events to be captured under the monitoring plan:

Adverse events greater than or equal to CTCAE Grade 3 will be recorded as the study team becomes aware of them. In addition, any protocol deviations and violations and unanticipated problems will be assessed for this study.

The person responsible for monitoring the data collected:

Principal Investigator
[name], MBA, FACS

The frequency of assessments/analysis of data or events captured by the monitoring plan:

In addition to the study team recording and assessing events in real time, the study monitor will review all events annually. The study team will also have a standing meeting once per month and schedule additional meetings as needed.

Time frame for reporting:

Events will be reported per IRB guidelines.

Stopping rules:

Action will be taken when a pattern occurs of events indicating an increase in the risks of study participation. A change in the risk/benefit ratio will be reported to the IRB.

Procedures/time frame for reporting outcomes of monitoring reviews:

Events meeting reporting requirements will be reported to the IRB per IRB guidelines.

Plans to monitor adherence to the IRB-approved protocol:

Protocol adherence will be reviewed during monthly study team meetings as well as by the study monitor during his annual review.

12. Administrative requirements

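### Sections 10.4 and 11.1 record only Grade 3 or higher adverse events, in conflict with Sections 10.1 and 10.2, so Grade 1–2 harms would not be counted or compared by arm

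*Combined protocol and SAP*

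**What the plan says.** **Recording rule.** Section 10.4: "Adverse events greater than or equal to CTCAE Grade 3 will be recorded as the study team becomes aware of them". The same sentence stands in the Data Safety Monitoring Plan, Section 11.1.

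**Definition and period.** Section 10.1 treats any unfavorable medical occurrence during participation as an adverse event, related or not. It adds: "Adverse event collection will begin at Day of Treatment Onset and continue through the last assessments". No grade limit is given.

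**Severity.** Section 10.2: "The severity of all adverse events will be assessed according to the following scale". It gives a three-level functional scale (mild, moderate, severe) and, separately, CTCAE Grades 1 to 5.

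**Schedule.** The Table 1 row "Adverse Events Monitoring" is marked at screening, at the 4-month evaluation and at the 8-month evaluation. The Phase I and Phase II columns are empty.

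**Contact.** Section 9.2: "Subjects are not seen between Botox treatments, but they are instructed to call with any concerns, questions, or adverse reactions". Section 3, under treatment and follow-up: "All patients will be followed by providers approximately once per month". That sentence goes on to describe therapy visits for retraining, and injection or a telephone evaluation for chemodenervation.

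**Expected harms.** For injections, Section 9.1 lists among others "infection, bleeding, bruising, weakness, pain where the shot was given, eyelid drooping, headache, nausea". For retraining it lists muscle or joint soreness or pain. It gives no rates and no grades.

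**The concern.** A definition that covers every event, a scale to rate every event and a rule that records only the severe ones cannot all be followed. Site staff would probably work from the recording rule, since it appears twice and is the operational instruction.

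The consequence falls on the harm comparison. Section 9.3 says the results can help guide treatment and support future guidelines. A choice between two established treatments turns partly on their tolerability, and events below Grade 3 would not be available by arm. A report of few or no adverse events could then reflect the recording threshold rather than the treatments. Section 11.1 also calls for action when events form a pattern suggesting increased risk. The adverse events feeding that judgment would be Grade 3 or higher only.

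**Working it through.** The documents give no adverse event rate, grade split or safety calculation, so there is no planned figure to reproduce. The check sets the provisions side by side and then gives an illustration on assumed values.

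**1. What each provision covers**

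| Place | Grades covered | When or how |
|---|---|---|
| 10.1 | All | Treatment onset to last assessments |
| 10.2 | All; Grades 1–5 defined | Not stated |
| 10.4 and 11.1 | Grade 3 or higher | When the team learns of the event |
| Table 1 | Not stated | Screening, 4 months, 8 months; method not stated |

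Sections 10.1 and 10.2 cannot be met under 10.4 and 11.1. Table 1 does not resolve this, because it does not say what is asked or which grades are kept. Its screening mark falls before collection begins under 10.1, which sends earlier occurrences to medical history.

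**2. Where the listed harms would fall**

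Section 10.2 reserves Grade 3 for events that are severe, medically significant or disabling, that call for hospitalization, or that limit self-care. Section 9.1 separates the very rare serious effects of injection from its other listed effects. Bruising, injection-site pain, eyelid drooping, dry eyes, headache and soreness would often sit below Grade 3. This is an inference from the type of harm.

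**3. Illustration (assumed values)**

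Input from Section 8.2: 18 participants per arm. Assumed: a risk p of any adverse event between 10% and 50% per participant, and a share s of affected participants reaching Grade 3 or higher between 1% and 20%.

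- Participants affected per arm: 18 × p, from 18 × 0.10 = 1.8 to 18 × 0.50 = 9.0.
- Participants recorded per arm: 18 × p × s, from 18 × 0.10 × 0.01 = 0.02 to 18 × 0.50 × 0.20 = 1.8.
- Chance that an arm records none: (1 − p × s)^18, from (1 − 0.10)^18 = 0.15 to (1 − 0.001)^18 = 0.98.

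The share not recorded is 1 − s, or 80% to 99%. It only restates the assumption on s and is not evidence about this trial.

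**4. Contact in Phase I**

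On Section 3's account, each arm has about four contacts in four months. On Section 9.2's account, an injection participant is not seen until the next treatment, and Section 1.2 puts re-injection at three to four months. The treating physician and coordinator are unblinded (Section 3). The first four months matter most here, because both arms receive both treatments afterwards.

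Lowering the grade threshold without a common question would leave this risk in place. Suppose, as an assumption, a true any-grade risk of 30% in both arms and 90% detection in one arm. Expected counts are then 18 × 0.30 × 0.90 = 4.9 in that arm, against the following in the other:

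- 90% detection: 4.9
- 70% detection: 18 × 0.30 × 0.70 = 3.8
- 50% detection: 18 × 0.30 × 0.50 = 2.7
- 30% detection: 18 × 0.30 × 0.30 = 1.6

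Nothing in the documents says which value applies, or which arm would be lower.

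**The case against.** The strongest reply is that both treatments are established, safety is not among the endpoints in Section 2, and a Grade 3 threshold can be a proportionate choice. That stands as a reason not to rank the point higher. It does not explain Sections 10.1 and 10.2, and the protocol does not give proportionality as its reason.

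There are also other channels. Section 11.1 adds: "In addition, any protocol deviations and violations and unanticipated problems will be assessed for this study". These carry no grade limit. Under Section 10.1, however, an unanticipated problem must be unexpected in severity, nature or frequency. Harms already listed are not unexpected in nature, and an unexpected frequency is hard to see if milder events go unrecorded. Interviews before treatment, at 4 months and optionally at 8 months cover experience with treatment, and withdrawals for adverse events are documented (Section 7.3). Neither gives a tabulation of harms by arm.

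A reader might infer more than the documents support:

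- *That events are caught only by chance.* Table 1 schedules monitoring at 4 and 8 months in both arms, and Section 3 gives everyone roughly monthly contact. The gap is that neither says what is asked.
- *That ascertainment does differ by arm.* Section 9.2 may mean only that there is no in-person visit, which is compatible with Section 3's telephone evaluation. It is a risk, not a finding.
- *That nearly all harms would be lost.* No rates or grades are stated.
- *That the mild and moderate categories must stay empty.* The functional scale is separate from the CTCAE grade, so a Grade 3 event could be rated moderate. Only Grades 1–2 are excluded.
- *That an upper confidence bound after zero events measures the defect.* Such a bound depends on the number of participants and would be the same under any recording rule.

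**Conclusion.** The conflict is real and rests on the text alone: 10.4 and 11.1 cannot be followed together with 10.1 and 10.2, and Table 1 leaves its monitoring undefined. If 10.4 governs, the recorded Grade 1–2 count is zero by rule in both arms, and those events are absent from the harm comparison and from the Section 11.1 trigger. How many events that is cannot be derived from the documents. That it includes many of the harms in Section 9.1 is probable from their nature. Differential ascertainment in Phase I is a possible further problem of unknown direction. The SFGS primary analysis is unaffected. The point is worth correcting because harms not recorded prospectively cannot be reliably recovered later, but it does not threaten the main result.

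**What to change.** 1. Reconcile Sections 10.1, 10.2, 10.4 and 11.1 and the Table 1 adverse event row, so that definition, grades, period and time points agree.
2. In 10.4 and 11.1, record events of any grade with one short fixed checklist of the harms already listed in 9.1. Ask it with the same wording in both arms at the existing monthly contacts, by visit or telephone, and at the 4- and 8-month evaluations.
3. Reconcile the descriptions of contact in Sections 3 and 9.2.
4. Leave reporting under IRB guidelines as it is.

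The cost is protocol wording, a one-page checklist, and a few minutes plus some data entry per contact. Steps 1 and 3 should come first, because the estimate of small cost assumes that the monthly contacts in Section 3 take place in both arms.

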11.1. Data Safety Monitoring Plan

The type of data or events to be captured under the monitoring plan:

Adverse events greater than or equal to CTCAE Grade 3 will be recorded as the study team becomes aware of them. In addition, any protocol deviations and violations and unanticipated problems will be assessed for this study.

The person responsible for monitoring the data collected:

Principal Investigator
[name], MBA, FACS

The frequency of assessments/analysis of data or events captured by the monitoring plan:

In addition to the study team recording and assessing events in real time, the study monitor will review all events annually. The study team will also have a standing meeting once per month and schedule additional meetings as needed.

Time frame for reporting:

Events will be reported per IRB guidelines.

Stopping rules:

Action will be taken when a pattern occurs of events indicating an increase in the risks of study participation. A change in the risk/benefit ratio will be reported to the IRB.

Procedures/time frame for reporting outcomes of monitoring reviews:

Events meeting reporting requirements will be reported to the IRB per IRB guidelines.

Plans to monitor adherence to the IRB-approved protocol:

Protocol adherence will be reviewed during monthly study team meetings as well as by the study monitor during his annual review.

12. Administrative requirements

